2. SPONSORSHIP

None, initiative study

6. HISTORY OF CHANGES

Version	Approval Date	Summary of Changes
Version 1.0	01.11.2023	Initial Draft
Version 1.1	20.03.2024	Changes made regarding the development of the information booklet

7. PROTOCOL SYNOPSIS

Study Title	Assessment of the left ventricle reverse remodeling outcomes in patients with aortic valve insufficiency after surgical correction
Sponsor	Investigator-Initiated Study
Study Phase	Phase III
Hypothesis	We hypothesize that surgical correction of functional mitral regurgitation during interventions for chronic aortic valve insufficiency in patients with significant dilatation of the left heart chambers affects the reverse remodeling of the left ventricle in the postoperative period.

Research objectives and tasks	
Research objective:
 
To assess myocardial reverse remodeling in patients with significant left ventricular dilation caused by chronic aortic regurgitation, depending on the degree of mitral valve insufficiency and surgical approach.
 
Main objectives of the study:
 
1. To evaluate the short-term and long-term outcomes of aortic valve replacement for aortic valve insufficiency in patients with significant left ventricular dilation2. To compare the results of myocardial reverse remodeling depending on the strategy regarding functional mitral valve insufficiency at 3 and 12 months post-surgery3. To determine preoperative predictors of an unfavorable left ventricle function and architecture recovery prognosis.4. Assess the patients life quality 12 months after surgery5. Develop a clinical protocol for simultaneous surgical treatment of mitral regurgitation during aortic valve replacement in patients with significant left ventricular myocardial remodeling caused by chronic aortic regurgitation
Study design	This study is a multicenter, comparative, prospective

Inclusion criteria	
1. Age over 18 years2. Proposed primary elective surgical intervention for chronic aortic regurgitation3. Presence of functional mitral regurgitation4. Left Ventricular End-Diastolic Volume 250 ml\geq
Exclusion criteria	
1. Infectious endocarditis2. Previous myocardial infarction3. Necessity for simultaneous myocardial revascularization4. Acute aortic regurgitation5. Previously established left ventricular dilation not associated with the development of aortic regurgitation6. Lack of informed consent
Number of study subjects	120 patients

Investigated procedure	
It is planned to study the initial and long-term results of left ventricle reverse remodeling in patients with aortic regurgitation, depending on the strategy chosen for the correction of functional mitral regurgitation and its severity.

Duration of observation	12 months after surgical treatment
Methods of statistical evaluation	
The determination of the significance of differences between quantitative data of unrelated samples will be carried out using the Student's t-test under the condition of normal distribution; in the case of non-normal distribution, the Mann-Whitney test, White's test, Van der Waerden test, and Kolmogorov-Smirnov test are planned to be used. In the case of analyzing the significance of differences in quantitative data in related samples with a normal distribution, the paired Student's t-test is planned to be used; in the case of non-normal distribution, the Wilcoxon test and sign test will be used. Qualitative data analysis will be performed using the χ^2 test and the McNemar test. To assess the reliability of the relationship between quantitative data, regression analysis, Pearson's correlation coefficient, Spearman's rank correlation coefficient, and Kendall's correlation coefficient are planned to be used. Descriptive and analytical statistical methods will be finalized after analyzing the sample size. To eliminate the influence of differences in baseline clinical parameters on the study outcome, a propensity score matching analysis (PSM) is planned between the ordinary 'Unmatched' groups using the nearest neighbor matching method for 1:1 pair matching.
 
Demographic data and clinical indicators will be presented using descriptive statistics (absolute indicators and percentage shares for categorical variables, or mean \pm standard deviation for normally distributed continuous variables; for continuous variables with non-normal distribution, the median and interquartile range will be specified). The significance of differences in repeated measurements will be analyzed using ANOVA.

Sample size	
Considering a clinically significant difference in left ventricle volumes 12 months after surgery, equal to 15 ml/m^2, with a power of 80% and alpha of 5%, the sample size should be at least 64 patients in each group.
 
The sample size usually depends on the standard deviation, which is determined based on the results of similar studies or, more often, a pilot study. Approximate indicators will be obtained by February 2024 after analyzing the RCHC sample within the framework of the dissertation research.

--------------------	---

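### The mitral-strategy comparison of EDV reduction rests on covariate-free tests and 1:1 matching alone; adding baseline EDV to the matched comparison and a baseline-adjusted model on the whole analysis population is a cheap improvement

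*Protocol*

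**What the plan says.** One of the main objectives in the synopsis (Protocol section 7) is "To compare the results of myocardial reverse remodeling depending on the strategy regarding functional mitral valve insufficiency at 3 and 12 months post-surgery". Section 11.1 describes a prospective cohort and no randomisation is mentioned. Section 9.1 leaves the mitral decision to the surgeon at operation. The first primary endpoint in section 10.2 is reduction of EDV at 3 and 12 months.

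The synopsis entry on statistical methods assigns tools as follows.

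- Between groups: "The determination of the significance of differences between quantitative data of unrelated samples will be carried out using the Student's t-test" if the data are normal, otherwise the Mann-Whitney, White, Van der Waerden or Kolmogorov-Smirnov test.
- Baseline differences: "To eliminate the influence of differences in baseline clinical parameters on the study outcome, a propensity score matching analysis (PSM) is planned", "using the nearest neighbor matching method for 1:1 pair matching". No caliper, replacement rule or covariate list is given.
- Regression: "To assess the reliability of the relationship between quantitative data, regression analysis" is listed next to correlation coefficients, as a tool for association.
- Repeated values: "The significance of differences in repeated measurements will be analyzed using ANOVA", with no baseline covariate named.
- Status: "Descriptive and analytical statistical methods will be finalized after analyzing the sample size".

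Baseline EDV will be known for every patient. It is an eligibility measurement (section 11.2.1), and echocardiography is scheduled at Examination 1 (Table 1 and section 12.4.6).

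**The concern.** When a surgeon chooses the strategy, the groups may well differ in ventricular size before operation. A larger ventricle also has more volume to lose, so a t-test or rank test on the reduction can turn a baseline difference into an apparent effect of strategy. A repeated-measures ANOVA that counts the baseline among its repeated values compares changes and has the same weakness.

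Matching does address measured imbalance. But 1:1 matching without replacement keeps at most twice the smaller group, and a plain t-test on the matched pairs makes no use of baseline EDV to reduce residual variance. The trial has little to spare: the synopsis plans 120 patients in total, against 2 × 64 = 128 implied by its own sample-size entry.

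The protocol names no model that uses all patients and holds baseline EDV fixed. At stake are some bias in the unmatched result and avoidable loss of precision in the matched one.

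**Working it through.** **The plan's own figure.** The sample-size entry says "the sample size should be at least 64 patients in each group" for a 15 ml/m² difference, 80% power and alpha 5%. It gives no SD and no sidedness. Assuming a two-sided t-test, 64 per group solves to SD 30.06 ml/m². Going forward, SD 30 gives 80.1% power at 64 per group and 77.5% at 60. The stated number thus fits a plain two-sample test without covariates. I take 12-month SD S1 = 30 as an assumption and 60 per group from the total of 120.

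**Unmatched test, closed form.** Let S0 be the baseline SD and ρ the correlation between baseline and 12 months. Neither is in the protocol.

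- SD of the reduction = √(S0² + S1² − 2ρ·S0·S1)
- Within-group slope = ρ·S1/S0
- Bias from a 10 ml/m² baseline gap = (1 − slope) × 10
- Residual SD of the adjusted model = S1·√(1 − ρ²)

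Example, S0 = 30 and ρ = 0.5: SD of reduction = √(900 + 900 − 900) = 30; bias = (1 − 0.5) × 10 = 5; adjusted SD = 30 × √0.75 = 26.0. Powers below are for a 15 ml/m² effect with no imbalance, by noncentral t.

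| S0 | ρ | Bias with gap of 10 (ml/m²) | False positives | Power, unadjusted reduction | Power, adjusted |
|---|---|---|---|---|---|
| 30 | 0.3 | 7.0 | 19% | 63% | 81% |
| 30 | 0.5 | 5.0 | 15% | 78% | 88% |
| 30 | 0.7 | 3.0 | 11% | 94% | 97% |
| 25 | 0.3 | 6.4 | 18% | 70% | 81% |
| 25 | 0.5 | 4.0 | 12% | 83% | 88% |
| 25 | 0.7 | 1.6 | 7% | 96% | 97% |
| 20 | 0.3 | 5.5 | 16% | 76% | 81% |
| 20 | 0.5 | 2.5 | 8% | 87% | 88% |
| 20 | 0.7 | −0.5 | 5% | 97% | 97% |

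The adjusted powers assume that strategy is unrelated to the covariates. If the covariates explain a share R² of strategy, the variance is divided by 1 − R². At S0 = 30 and ρ = 0.5 with three covariates, R² of 0, 0.2, 0.3 and 0.5 gives 88, 80, 75 and 60%.

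**Patients lost to matching.** Without replacement (assumed), the minimum loss is 120 − 2 × (smaller group): 0 at 60/60, 20 at 50/70, 40 at 40/80 and 60 at 30/90.

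**Simulation.** n = 120, ρ = 0.5, 1,500 runs per cell (Monte Carlo error at most √(0.25/1500) = 1.3 points). MR grade 1/2/3 in 35/40/25%, adding 4 ml/m² per grade at 12 months; two centres. Strategy depends on measured baseline EDV and grade, with 9, 18 or 33% of it explained. Matching is greedy 1:1 with a caliper of 0.2 SD of the logit, which is my assumption and not the plan's. Results for SD 30/30:

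| | 9% | 18% | 33% |
|---|---|---|---|
| Unmatched t-test: bias (ml/m²) | 4.4 | 5.6 | 4.7 |
| Unmatched t-test: false positives | 12% | 16% | 14% |
| Adjusted model, all patients: false positives | 4.5% | 5.0% | 6.5% |
| Adjusted model, all patients: power | 80% | 76% | 67% |
| Matched t-test: power | 56% | 53% | 38% |
| Matched and adjusted for baseline EDV: power | 65% | 62% | 50% |
| Pairs kept | 35 | 32 | 26 |

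Bias of the adjusted model and of the matched, EDV-adjusted analysis is within 0.3 ml/m². Adding baseline EDV to the matched analysis gains 65.3 − 55.7 = 9.6, 62.2 − 52.6 = 9.6 and 49.5 − 37.9 = 11.6 points. With SD 20/30 the unmatched test is nearly unbiased (0.7, 0.6, −0.7; 6, 5, 5% false positives), but the adjusted model still has more power than the matched and adjusted one: 79 v 64, 75 v 61 and 68 v 51%.

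**A different selection mechanism.** Suppose strategy follows true ventricular size, which echo measures with error (SD 30/30, ρ = 0.5, no true effect, log-odds of 0.4, 0.6 or 0.8 per SD of true size). The unadjusted reduction then has bias of about 0, 0.3 and 0.2 ml/m² and 5% false positives. The adjusted model has bias of 4.1, 6.3 and 7.9 ml/m² and 14, 23 and 36% false positives. If MR grade also drives strategy, the biases are 0.8, 1.9 and 3.4 (unadjusted) against 3.9, 5.9 and 8.0 (adjusted). Matching shows the same latent-size bias as the adjusted model.

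**The case against.** A reader might infer that the unadjusted reduction is simply wrong and should be replaced. The documents do not support that. The bias in its disfavour assumes that strategy depends on the measured baseline value. If strategy follows true size read with error, the ranking reverses, as the last calculation shows, and nothing in the protocol says which mechanism holds. This objection stands, and it is why the unadjusted result should be kept.

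A reader might also infer that confounding is left uncontrolled, or that matching is the wrong tool. It is not: matching is planned for exactly this purpose and does deal with measured imbalance. The power lost to it depends in part on a caliper that the plan does not state. In a separate run of the same design (SD 30/30) without a caliper, about 44, 45 and 48 pairs remained and matched, EDV-adjusted power was 78, 81 and 90%, against 82, 79 and 72% for the adjusted model. Residual bias was then 0.2, 1.2 and 2.6 ml/m², so some of that power may be bias. The choice is one of bias against variance and not a plain loss.

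It can further be said that model form belongs in a statistical analysis plan, that the t-test sentence is generic, and that the protocol leaves its methods to be finalised. All true, and a plan not at hand may already contain such a model. But the protocol does name its between-group tests and its confounder control, so the point concerns a stated choice and not a missing detail.

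Finally, it would be tempting to ask for a model on every operated patient. Section 11.2.3 excludes patients with certain events in the first 12 months, so that would change the analysis population. The proposal here does not.

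**Conclusion.** The point holds as a cheap improvement, with medium confidence. For a non-randomised strategy comparison, the protocol names covariate-free tests and 1:1 matching as the only confounder control. The protocol has already committed to conditioning on baseline parameters by matching, which shares the adjusted model's exposure to error in measured EDV. Given that commitment, using baseline EDV in the matched analysis gains about 10 to 12 points of power in the scenario simulated. A model on all patients gains more where groups are unequal or a caliper is used.

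The size is conditional throughout. SD, correlation, baseline gap, group split, grade effect and caliper are all assumed. The simulated outcome was linear, which favours the adjusted model, and complete non-overlap in MR grade was not simulated. The gain over the unadjusted test nearly vanishes when baseline SD is well below the 12-month SD and correlation is 0.5 or more, and it shrinks or disappears if strategy is strongly tied to the covariates. The figures are in ml/m², as in the sample-size entry, whereas section 10.2 states EDV reduction without indexing.

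**What to change.** In the synopsis entry on statistical methods, for the comparison of EDV by mitral strategy:

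1. Keep the 1:1 matched analysis, and adjust it for baseline EDV.
2. Add an ANCOVA of EDV on strategy, baseline EDV and centre, or a mixed model over 3 and 12 months read at 12 months. Use all patients in the protocol's analysis population, including those left unmatched. Add preoperative MR grade where the strategies overlap on it, but not in analyses where MR severity is itself the exposure, as in the primary objective of section 10.1.
3. Keep the unadjusted reduction as a descriptive or supporting result.
4. Report how far baseline EDV and MR grade overlap between strategies.
5. Name one analysis as primary before the data are seen. The choice can be left to the investigators.

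The cost is analysis wording; no new measurement, visit or patient is needed. The downside is that the model assumes linearity, extrapolates where MR grades do not overlap, and relies on strategy depending on the measured baseline value. If that last assumption fails, both the adjusted and the matched estimates can be more biased than the unadjusted change, which is the reason for item 3.

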11.1 General Provisions

A multicenter controlled comparative prospective cohort study is planned.

It is known that chronic aortic valve insufficiency leads to significant remodeling of the left ventricle and development of functional mitral regurgitation. On one hand, residual mitral regurgitation may complicate the postoperative period by increasing the preload on the left ventricle; however, a dilated left ventricle after surgical correction of the aortic defect still requires supraphysiological preload during the most vulnerable period of early rehabilitation. As the volume of the left ventricle regresses, functional mitral regurgitation is also capable of regressing. A significant scientific task is to address the role of functional mitral regurgitation in the reverse remodeling of the left ventricle after correction of chronic aortic valve insufficiency.

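### Student's t-test for unmatched groups is conditioned on normality alone; naming Welch's test would protect the 5% level at no cost if group sizes and spreads both differ

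*Protocol*

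**What the plan says.** Protocol section 7 (synopsis, methods of statistical evaluation) states that the comparison of quantitative data in unrelated samples "will be carried out using the Student's t-test under the condition of normal distribution". The alternatives depend on the same single condition: "in the case of non-normal distribution, the Mann-Whitney test, White's test, Van der Waerden test, and Kolmogorov-Smirnov test are planned to be used". Neither an equal-variance check nor an unequal-variance version of the t-test is named.

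Three other statements bear on the point.

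- **Design.** Section 11.1: "A multicenter controlled comparative prospective cohort study is planned". Section 9.1 describes the mitral decision as one that the surgeon faces during the operation. The text fixes no allocation ratio.
- **Matching.** The synopsis adds propensity score matching "between the ordinary 'Unmatched' groups using the nearest neighbor matching method for 1:1 pair matching".
- **Size.** The synopsis gives 120 patients in total, and its sample-size paragraph says that "the sample size should be at least 64 patients in each group", for a 15 ml/m² difference with 80% power and 5% alpha. No SD is stated.

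The methods paragraph also says that the methods are still to be finalised.

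**The concern.** Student's test pools the two sample variances. With equal group sizes this does no harm. With unequal sizes, the pooled variance is dominated by the larger group. If the smaller group is the more variable one, the standard error is too small and false positives exceed 5%. If the larger group is the more variable one, the standard error is too large and real differences are missed.

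A randomised trial usually keeps group sizes close by design. Here the groups follow the chosen mitral strategy, and the plan itself expects baseline differences, which is why it matches. The listed alternatives are triggered by non-normality only, so they would not come into play for normal data with unequal variances. What is at stake is the crude, unmatched comparison of quantitative outcomes, including the co-primary reduction in end-diastolic volume.

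**Working it through.** **Inputs.** From the protocol: total 120, alpha 5%, difference 15 ml/m², at least 64 per group. Assumed, because the documents do not say: two groups, two-sided testing, normal data, the group split, and the SDs.

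**The plan's own figure.** The 64 per group cannot be derived from what is stated, because the SD is missing. It fits an SD of about 30 ml/m² (standardised difference 15/30 = 0.5): the normal approximation gives 63 and the t-based formula gives 63.8, rounded up to 64. At SD 25 or 35 the normal approximation would give 44 or 86. I therefore take 30 ml/m² as the reference SD. The error rates below depend only on the SD ratio and the split, not on this level.

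**Why size and spread must both differ.** The true variance of the mean difference is s₁²/n₁ + s₂²/n₂. Student's test estimates, on average, [((n₁−1)s₁² + (n₂−1)s₂²)/(n₁+n₂−2)] × (1/n₁ + 1/n₂). The two agree if n₁ = n₂ or if s₁ = s₂. Let r be the square root of true over estimated variance. The actual error is then about 2 × [1 − Φ(1.96/r)].

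*Smaller group more variable: 40 patients with SD 45, 80 with SD 30.*
- True: 2025/40 + 900/80 = 61.9.
- Student's: (39×2025 + 79×900)/118 × (1/40 + 1/80) = 1271.8 × 0.0375 = 47.7.
- r = √(61.9/47.7) = 1.14, so the error is about 8.5%.

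*Larger group more variable: 40 patients with SD 30, 80 with SD 45.*
- True: 900/40 + 2025/80 = 47.8.
- Student's: (39×900 + 79×2025)/118 × 0.0375 = 62.0.
- r = 0.88, so the error is about 2.6%.

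**Simulation** (normal data, no true difference, 1,000,000 runs per cell). Student's actual error at nominal 5%:

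| Split | Smaller group's SD ×1.5 | Smaller group's SD ×2 | Larger group's SD ×1.5 | Larger group's SD ×2 |
|---|---|---|---|---|
| 60/60 | 5.0% | 5.1% | 5.0% | 5.1% |
| 56/64 | 5.6% | 6.0% | 4.5% | 4.2% |
| 50/70 | 6.7% | 7.7% | 3.7% | 3.1% |
| 40/80 | 8.5% | 11.0% | 2.6% | 1.7% |
| 30/90 | 10.7% | 15.2% | 1.8% | 0.8% |

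In the 60/60 row, where neither group is smaller, the columns simply give the two directions. Welch's test gave 5.0% in every cell. With equal SDs, Student's test also gave 5.0% at every split.

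**Power for 15 ml/m² at 40/80.**
- Larger group SD 45, smaller SD 30: Student 47%, Welch 58%.
- Larger group SD 30, smaller SD 45: Student 57%, Welch 47%. Student's advantage here comes from running at 8.5% instead of 5%.
- Both SDs 30: Student 72.6%, Welch 72.2%. This is the price of Welch when it is not needed.

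**The case against.** The strongest reply is that nothing has been shown to be wrong. Pooled versus unequal variance is a detail often settled in a statistical analysis plan, and the synopsis itself calls its methods provisional. The only group size in the documents is at least 64 in each group. A total of 120 cannot reach 2 × 64 = 128, but the splits nearest the plan are about 60/60 or 56/64, where Student's error is 4-6%. The 1:1 matched sets are equal in size, and there the test keeps its level. In the crude comparison, confounding by the choice of strategy is the larger threat, and Welch's test does nothing about it.

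Most of this stands, and it sets the grade. It does not remove the point: the protocol is not silent but names a specific test with an incomplete condition. The target of 64 is a minimum and not an allocation rule, and the plan does not say that matching replaces the unmatched comparison.

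Two stronger readings are tempting. A reader might infer from the 250 ml entry threshold that end-diastolic volume has a long upper tail, so that spreads must differ. The threshold applies to baseline volume in ml, whereas the endpoint is a reduction and the planning difference is in ml/m² at 12 months. Marked skewness would also send the data to the rank tests under the plan's own rule. A reader might also want robust standard errors for a regression of outcome on mitral strategy, but the protocol specifies no such model.

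**Conclusion.** The point holds as a minor, cost-free improvement to the unmatched comparisons. Student's test goes wrong only if group sizes and spreads differ together. Under assumed SD ratios of 1.5 to 2 and 120 patients, the departure is negligible to slight near the planned sizes (4-6% at 56/64). It becomes material only at clearly uneven splits (2-11% at 40/80, 1-15% at 30/90). The documents state neither an SD nor an expected split, so they do not support a claim that the 5% level will be lost or that the primary result will be wrong. Comparisons within 1:1 matched sets of equal size are outside the point.

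**What to change.** In the synopsis paragraph on statistical methods, replace Student's t-test for unrelated samples by the Welch (unequal-variance) t-test, and say that it is used without a preliminary test of variances. Choosing between the two tests after such a check would add a data-dependent step for no gain.

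The cost is one sentence, with no extra patients or data. If the SDs prove equal, the power loss at 40/80 is about 0.4 percentage points (72.6% to 72.2%), and at 60/60 the power is the same to the first decimal (77.5%).

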10.1 Objectives

Primary objective:

1. To assess the impact of functional mitral regurgitation on the rate and degree of reverse myocardial remodeling in patients with significant left ventricular dilation against the background of chronic aortic valve insufficiency after surgical correction of the aortic defect.

Secondary objectives:

1. To assess the relationship between the severity of preoperative functional mitral valve insufficiency and the patient's life quality 12 months after surgery.

Research objectives:

1. To assess the relationship between severity of functional mitral regurgitation and diastolic dysfunction of the left ventricle at 3 and 12 months after surgical correction of aortic regurgitation.
2. To assess the relationship between the severity of functional mitral regurgitation and the dynamics of left atrial volume, evaluated by transthoracic ECHO-CG, at 3 and 12 months after surgical correction of aortic regurgitation.

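### The protocol names no adjusted analysis for the section 10.1 objectives on functional mitral regurgitation, so an association could reflect ventricular size or the mitral operation instead

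*Protocol*

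**What the plan says.** **Exposure.** The primary objective in section 10.1 is "To assess the impact of functional mitral regurgitation on the rate and degree of reverse myocardial remodeling". The secondary objective is "To assess the relationship between the severity of preoperative functional mitral valve insufficiency and the patient's life quality 12 months after surgery". The two research objectives are "To assess the relationship between severity of functional mitral regurgitation and diastolic dysfunction of the left ventricle" and "To assess the relationship between the severity of functional mitral regurgitation and the dynamics of left atrial volume", each at 3 and 12 months. The synopsis states the overall aim as remodeling "depending on the degree of mitral valve insufficiency and surgical approach". Inclusion criterion 3 (section 11.2.1) requires functional MR in every patient.

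**Methods.** The synopsis (Methods of statistical evaluation) says of relationships between quantitative data that "regression analysis, Pearson's correlation coefficient, Spearman's rank correlation coefficient, and Kendall's correlation coefficient are planned to be used". It also lists two-sample tests, paired tests, chi-square, McNemar and ANOVA. It names no covariates, ties no method to an objective, and says that the methods will be finalized later.

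**Confounding.** One step is given: "To eliminate the influence of differences in baseline clinical parameters on the study outcome, a propensity score matching analysis (PSM) is planned". Its form is nearest-neighbor pairing, one to one, of two groups. The groups are not defined and the score variables are not listed.

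**Design and endpoint.** Section 11.1 describes a prospective cohort and says that aortic insufficiency leads both to LV remodeling and to functional MR. The first primary endpoint (section 10.2) is the reduction in LV EDV at 3 and 12 months.

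**The concern.** In a non-randomized cohort, the degree of MR comes with other features of the patient. Two of them matter here.

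- **LV size.** On the protocol's own account, LV remodeling and functional MR arise from the same lesion. Reduction in EDV is baseline minus follow-up. Anything correlated with baseline EDV will therefore tend to correlate with the reduction, even if it has no influence on follow-up EDV once baseline is known.
- **The mitral operation.** Some patients will have the mitral valve corrected and others will not. Section 9.3 treats these as different loading states for the ventricle. If the choice is related to severity, an unadjusted severity association mixes the two states. Matching on baseline variables does not separate them, because the operation comes after baseline.

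The matching step also does not carry over to an ordered exposure. Pairs need exactly two groups, and no two-level split of MR severity is given.

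At stake is whether a reported link between MR severity and remodeling, atrial volume, diastolic function or quality of life can be read as being about MR at all.

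**Working it through.** The protocol gives no figure for this point. Its sample-size statement concerns a difference between two groups, not an association with a graded exposure. The check therefore asks how often a named unadjusted method would find an association when severity has no effect of its own.

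**Inputs**
- n = 120 (synopsis, number of subjects).
- alpha = 5%, taken as two-sided (synopsis, sample size; sidedness not stated).
- a = correlation of MR severity with baseline EDV. Assumed: 0.2, 0.3, 0.5.
- ρ = correlation of baseline with 12-month EDV. Assumed: 0.5, 0.7.
- Equal SDs at baseline and 12 months. Assumed.
- No effect of severity on 12-month EDV given baseline EDV (the null case).

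**Step 1: induced correlation.** Under the null case, severity correlates aρ with 12-month EDV. With SD σ at both times and severity standardized, its covariance with the reduction is σa(1 − ρ), and the variance of the reduction is 2σ²(1 − ρ). Hence

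r = a(1 − ρ) / √(2(1 − ρ)) = a √((1 − ρ)/2).

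**Step 2: rejection probability.** By Fisher's transformation, z = atanh(r) × √(n − 3) = atanh(r) × √117 = atanh(r) × 10.817, and P(reject) = Φ(z − 1.96) + Φ(−z − 1.96).

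For a = 0.3 and ρ = 0.5: r = 0.3 × √0.25 = 0.15, z = 0.1511 × 10.817 = 1.635, and P = Φ(−0.325) + a negligible term = 37%.

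| a | ρ | r | z | P(reject) |
|---|---|---|---|---|
| 0.2 | 0.7 | 0.077 | 0.840 | 13% |
| 0.2 | 0.5 | 0.100 | 1.085 | 19% |
| 0.3 | 0.7 | 0.116 | 1.262 | 24% |
| 0.3 | 0.5 | 0.150 | 1.635 | 37% |
| 0.5 | 0.7 | 0.194 | 2.121 | 56% |
| 0.5 | 0.5 | 0.250 | 2.763 | 79% |

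**Step 3: does adjustment cure it?** A simulation of 3000 trials at a = 0.3 and ρ = 0.5 gave 37.4% rejections for the unadjusted correlation and 5.1% once baseline EDV was in the model.

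**Step 4: unequal SDs.** If the 12-month SD is k times the baseline SD, then r = a(1 − ρk)/√(1 + k² − 2ρk). With an assumed k = 0.8, a = 0.3 and ρ = 0.5, r = 0.3 × 0.6/√0.84 = 0.196, z = 0.199 × 10.817 = 2.15 and P = 58%. A smaller spread at follow-up makes the problem larger. A larger spread makes it smaller, and it vanishes at ρk = 1.

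**Step 5: graded MR with an operation.** A second simulation (2000 trials per scenario, n = 120) used a three-level grade and no direct MR effect. LV size correlated 0.5 with the outcome. The mitral operation was given to 10%, 50% and 85% of patients by rising grade. All of these are assumptions.
- LV size correlated 0.3 or 0.5 with latent severity and the operation had no effect: unadjusted Spearman rejected in 30% or 67%.
- Same, with the operation shifting the outcome by 0.5 SD in the same direction as LV size: 85% or 98%.
- Only the operation acts: 36%.
- Regression on grade, baseline LV size and operation: about 5% in every scenario.

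Adjusting for baseline removes the LV-size part. The operation part is separated only when the procedure is also taken into account.

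**The case against.** - **Covariates belong to a statistical analysis plan.** This stands in part. A reader might infer that the regression has no covariates or that baseline EQ-5D will go unused. The protocol says neither. The regression is simply unspecified, a plan may exist that is not at hand, and the methods are declared open. What remains is that every method the protocol does name for an association is unadjusted, and that its one confounding control is built for another kind of question.
- **Correlation is not the only option offered.** Correct. Group tests and ANOVA could compare severity groups. They are equally unadjusted.
- **Matching may suit the real question.** The hypothesis in the synopsis concerns surgical strategy, which is a two-group contrast. The primary objective says MR rather than severity, and section 11.1 also discusses residual MR. Matching on a two-level severity split, with LV size in the score, is not excluded. This is fair. But the groups are undefined, and no split is stated for the three objectives that name severity. No baseline score covers the operation.
- **Misattribution is not certain.** Agreed: it is a risk that depends on the final model. That more severe MR is operated on more often is plausible but not stated in the protocol.
- **The magnitude is assumed.** Agreed. It also presumes 120 complete cases despite the post-enrolment exclusions in section 11.2.3. The 250 ml entry limit may weaken the link between severity and baseline EDV. The formula covers a change score only, so it puts no number on the quality-of-life or diastolic objectives.

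**Conclusion.** The point holds as a gap that should be fixed. For the section 10.1 objectives, the protocol names unadjusted association measures and group tests, an unspecified regression, and a matching step that presupposes two undefined groups and cannot account for the mitral operation. With a reduction-in-EDV endpoint in a non-randomized cohort, following the named unadjusted methods would leave LV size and the mitral procedure as rival explanations for any association with MR.

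Under the stated assumptions (a from 0.2 to 0.5, ρ from 0.5 to 0.7, equal SDs, n = 120), the false-positive rate is about 13% to 79% against a nominal 5%. The protocol does not fix where in that range, or outside it, the trial would fall.

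The protocol does not support the stronger reading that the results will necessarily be misread as an effect of MR.

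**What to change.** **Main analysis.** For each severity objective in section 10.1, name as the main analysis a regression of the 3- and 12-month value on preoperative MR grade. Adjust it for the baseline value of the same outcome (EDV, left atrial volume, diastolic index or EQ-5D) and for baseline LV volume. For the EDV endpoint these two covariates are one and the same. State the exposure of the primary objective; since all patients enter with functional MR, preoperative grade is the natural reading. Keep the correlation coefficients as descriptive.

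**Supportive analysis.** Report the severity association also by mitral procedure (corrected or not). Say that conditioning on the procedure changes the estimand, because the procedure follows preoperative severity. A severity-by-procedure interaction may be poorly estimated in 120 patients and should not carry the conclusion.

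**Matching.** Define the two groups and keep this step for the contrast it serves.

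**Cost.** Wording, some extra analysis work and a few degrees of freedom. Echocardiography and EQ-5D are already scheduled at Examination 1, and features of the operation are recorded at Examination 2. No new data are needed.
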